7.1. Study Subjects

7.1.1. Analysis Sets

The primary analysis will be evaluated for the implanted population. The implanted population consists of all enrolled subjects who are actually implanted with a Mosaic or Hancock II device. To be considered implanted, the subject's device disposition form must show at least one device with a final disposition of "Implanted." Time zero begins at the date of the procedure.

7.2. General Methodology

All continuous variables will be summarized with means, standard deviations, medians, interquartile ranges, minimums, and maximums. Categorical variables will be summarized with frequencies and percentages.

For comparisons of categorical data between sub-groups, chi-square tests will be used unless there are expected cell counts of less than 5. In those cases, Fisher's exact test will be used. No multiplicity adjustments will be made to control the familywise Type I error rate. Caution needs to be taken when interpreting statistical significance or making statistical inference.

All statistical tests and/or confidence intervals, as appropriate, will be performed at $\alpha=0.05$ (2-sided), except when specified otherwise. All reported p-values greater than or equal to 0.001 will be rounded to three decimal places. P-values less than 0.001 will be displayed as "<0.001".

7.3. Center Pooling

The study will be conducted at up to 15 sites worldwide with approximately up to 7 sites in the US and up to 8 sites in Europe with a maximum of 110 total subjects enrolled. Per site there is no minimum enrollment requirement, however, a maximum of 20 enrolled subjects per site will be allowed. Data from all the sites will be pooled for the analyses.

7.4. Handling of Missing Data and Dropouts

Unless specified otherwise in each objective, no statistical techniques will be used to impute missing data. If a subject's data are missing for any reason, that subject will not be included in that portion of the analysis. The number of subjects included in each analysis will be reported so that the potential impact of missing data can be assessed.

In the case of partial dates, the general rule is as follows:

- If only the month and year are known, the event or assessment will be analyzed as if it occurred on the 15th of that month.
- If only the year is known, the event or assessment will be analyzed as if it occurred on June 30th of that year.

These resolutions of partial dates are subject to the restrictions that pre-procedure events and assessments must occur between the enrollment date and the procedure date, and post-procedure events and assessments must occur no earlier than the procedure date. If additional information about the partial dates might be known, for example, the event occurs after 15th of the month, then data may be analyzed as if it occurred on the 16th of the month.

7.5. Demographic and Other Baseline Characteristics

Descriptive statistics will be used to report demographic and clinical characteristics at baseline. Major baseline demographic and clinical variables will be summarized for the implanted populations. Information to be summarized includes, but is not limited to:

- Demographics (age, gender)
- Cardiovascular conditions and risk factors
- Previous cardiac interventions

7.6. Evaluation of Objectives

7.6.1. Primary Objective(s)

The primary objective of the study is to characterize the freedom from valve related death, re-intervention of, or explant related to the Mosaic and Hancock II valves with PEEK stent material in a patient population undergoing aortic or mitral valve replacement of his/her native aortic or mitral valve at 1 year post implant.

7.6.1.1. Hypothesis and/or Parameters to Be Estimated

No specific hypotheses have been set for the overall analysis of freedom from deaths, re-intervention, or explant related to the Mosaic and Hancock II valves with PEEK stent material. Kaplan-Meier estimates will be provided for freedom from death, re-intervention of, or explant related to the Mosaic and Hancock II valves with PEEK stent material with its lower 95% confidence interval at 1 year.

7.6.1.2. Endpoints

The primary endpoints are valve related death, re-intervention of, or explant related to the Mosaic and Hancock II valves with PEEK stent material at 1 year.

7.6.1.3. Data Collection and Analysis Methods

Death, re-intervention, or explant related to the Mosaic and Hancock II valves will be adjudicated by the Clinical Events Committee (CEC) and collected on the CEC form. CEC adjudication shall overwrite the Medtronic classification of the events or site classification of the events.

Kaplan-Meier method will be used for time to the first valve related death, re-intervention of, or explant of the study valve related to the Mosaic and Hancock II valves with PEEK stent material at 1 year after procedure. Subjects not experiencing the event through 1 year after procedure will be censored. One year is defined at timepoint of 365 days post procedure. The product-limit estimate of the event-free rate (or event rate), the number of subjects at risk, the number of subjects with event, the number of subjects censored, and the log-log transformed lower one-sided 95% confidence interval using the Greenwood standard error will be presented.

Specifically, Kaplan-Meier estimate is as follows.

$$\hat{S}(t_k) = \prod_{j=1}^k \left(1 - \frac{d_j}{n_j}\right)$$

Greenwood variance is estimated as below.

$$Var(\hat{S}(t_k)) = \hat{S}(t_k)^2 \sum_{j=1}^k \frac{d_j}{n_j(n_j - d_j)}$$

Pointwise one-sided lower 95% confidence interval at 365 days post procedure after log-log transformation (Kalbfleisch and Prentice; 1980) is as below.

$$\hat{S}(t)^{\exp(z_{\alpha} * tao)}$$

$$\text{where } tao = \frac{\sigma(\hat{S}(t))}{\hat{S}(t) * \log(\hat{S}(t))}$$

A Kaplan-Meier plot will also be presented.

This objective will be analyzed for the implanted population.

7.6.2. Secondary Objective(s)

The secondary objective of the study is to characterize the clinical performance of Mosaic and Hancock II valves containing PEEK stent material at 1 year post implant with regard to NYHA Functional Classification and hemodynamic performance.

7.6.2.1. Hypothesis and/or Parameters to Be Estimated

No specific hypotheses have been set for the analysis of hemodynamic performance of Mosaic and Hancock II valves containing PEEK stent material at 1 year post implant.

7.6.2.2. Endpoints

The clinical performance endpoints are:

- NYHA Functional Classification (at 1 year and annually thereafter through 3 years)
- Clinically acceptable hemodynamic performance obtained from echocardiography (at discharge or 30 days), 1 year and annually thereafter through 3 years) including:
 - effective orifice area (EOA)
 - effective orifice area index (EOAI)
 - peak pressure gradient
 - mean pressure gradient
 - performance index
 - cardiac output
 - cardiac index
 - valve regurgitation

7.6.2.3. Data Collection and Analysis Methods

NYHA data will be collected at baseline, 1 year and annually through 3 years on the site follow-up form. Echo data will be collected at baseline, discharge through 30 days, 1 year and annually through 3 years. All transthoracic (TTE) echoes will be analyzed by an echo core lab which will determine the values for the Hemodynamic Performance endpoints.

Data Collection Requirement	Assessment Intervals					
	Baseline	Implant	Discharge through 30 days	1 Year	Annually years 2-3	Exit
Window from implant	-45 days/-180 days for TTE	Date of Mosaic and Hancock II valves with PEEK material Implant	≤ 30 days	± 30 days	± 60 days	Date of Exit
Demographics	X					

Data Collection Requirement	Assessment Intervals					
	Baseline	Implant	Discharge through 30 days	1 Year	Annually years 2-3	Exit
Window from implant	-45 days/-180 days for TTE	Date of Mosaic and Hancock II valves with PEEK material Implant	≤ 30 days	± 30 days	± 60 days	Date of Exit
Physical Examination	X					
Pregnancy Test	X*					
Medical History	X					
NYHA Classification	X			X	X	
12-Lead ECG	X		X	X	X	
Blood Labs				X	X	
Transthoracic Echo (TTE)	X		X	X	X	
Transesophageal Echocardiogram (TEE)		X				
AE/Device Deficiency		X	X	X	X	X
Relevant Medications	X		X	X	X	
EuroScore II	X					
STS Risk Score	X					
Operative Information		X				
Protocol Deviations		X	X	X	X	X
Study Exit						X

*Pregnancy test is required for female subjects who are not exempt, see CIP section 10.3.1.

NYHA functional classification and echocardiographic (TTE) hemodynamic data will be summarized using descriptive statistics for continuous variables and frequency tables for discrete variables. NYHA functional class will be evaluated based on the percentage of subjects in each specific NYHA class at each follow-up time-point.

Hemodynamic Performance endpoints will be summarized as with continuous data. These data will be summarized by aortic and mitral position.

This objective will be analyzed for the Implanted population.

8. Validation Requirements

Validation requirements will follow SAS Programmers group guidance.

9. References

Kalbfleisch, J. D. and Prentice, R. L. (1980), *The Statistical Analysis of Failure Time Data*, New York: John Wiley & Sons.

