**Table 5. New York Heart Association (NYHA) Classification**

Class I	Subject with cardiac disease but without resulting limitations of physical activity. Ordinary physical activity does not cause undue fatigue, palpitation, dyspnea, or anginal pain.
Class II	Subjects with cardiac disease resulting in slight limitation of physical activity. They are comfortable at rest. Ordinary physical activity results in fatigue, palpitation, dyspnea, or anginal pain.
Class III	Subjects with cardiac disease resulting in marked limitation of physical activity. They are comfortable at rest. Less than ordinary physical activity causes fatigue, palpitation, dyspnea, or anginal pain.
Class IV	Subjects with cardiac disease resulting in inability to carry on any physical activity without discomfort. Symptoms of cardiac insufficiency or of the anginal syndrome may be present even at rest. If any physical activity is undertaken, discomfort is increased.

NYHA classification will be assessed at baseline and 1 through 3 year follow-up visits with the results recorded on the appropriate eCRF.

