### 14.2.3. Analysis Methods

No specific hypotheses have been set for the overall analysis of freedom from deaths, re-intervention, or explant related to the Mosaic and Hancock II valves with PEEK stent material. Historical control data are provided below for qualitative comparison.

1 year Endpoint	Control Value Freedom from $\pm$ Standard Error
Valve-related Death Mosaic  Hancock II 	$98.6 \pm 0.8$ $94.6 \pm 2.4$
Valve Related Reoperation Mosaic  Hancock II 	$99.1 \pm 0.6$ $100.0 \pm 3.6$
Valve-related Explant Mosaic  Hancock II 	$99.1 \pm 0.6$ $100.0 \pm 3.6$

Mosaic Mitral Bioprostheses 16-year clinical compendium

Medtronic Hancock II Long-Term Clinical Study MVR results provided in Instructions for Use

Kaplan-Meier method will be used for the time to the first valve related death, re-intervention of the study device, or explant related to the Mosaic and Hancock II valves with PEEK stent material at 1 year after procedure. Subjects not experiencing the event through 1 year after procedure will be censored. One year is defined at time point of 365 days post procedure. The product-limit estimate of the event-free rate (or event rate), the number of subjects at risk, the number of subjects with event, the number of subjects censored, and the log-log transformed lower one-sided 95% confidence interval using the Greenwood standard error will be presented. Subjects will be censored at their last visit, or death/explant/exit.

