##### **14.3.1.1. Analysis Methods**

NYHA functional classification and echocardiographic hemodynamic data will be summarized using descriptive statistics for continuous variables and frequency tables for discrete variables. NYHA functional class will be evaluated based on the percentage of subjects in each specific NYHA class at each follow-up time-point.

Hemodynamic performance will be qualitatively compared with historical clinical performance data for Mosaic and Hancock II valves from literature as well as current guidelines for the treatment of aortic and mitral valve disease to evaluate clinically acceptable performance.

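### The planned NYHA analysis gives class percentages at each follow-up visit only: it does not pair them with the baseline class already collected, names no NYHA reference value, and lets deaths and explants leave the denominator

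*SAP*

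**What the plan says.** - **Collection.** Protocol 10.3.3: "NYHA classification will be assessed at baseline and 1 through 3 year follow-up visits". SAP 7.6.2.3 agrees: "NYHA data will be collected at baseline, 1 year and annually through 3 years on the site follow-up form".
- **Endpoint.** Protocol 6.2.2 and 14.3.1 and SAP 7.6.2.2 define it as NYHA class at years 1, 2 and 3. Baseline is not part of the definition.
- **Analysis.** SAP 7.6.2.3: "NYHA functional class will be evaluated based on the percentage of subjects in each specific NYHA class at each follow-up time-point". Protocol 14.3.1.1 carries the same sentence. Neither document mentions a shift table, a change from baseline or a definition of improvement for NYHA.
- **Reference values.** Protocol 14.3.1.1 plans an external comparison for hemodynamics: "Hemodynamic performance will be qualitatively compared with historical clinical performance data for Mosaic and Hancock II valves from literature". For the primary endpoint, Protocol 14.2.3 says "Historical control data are provided below for qualitative comparison", and that table covers valve-related death, reoperation and explant. Neither covers NYHA, and the SAP names no historical comparator.
- **Position.** SAP 7.6.2.3 splits results by aortic and mitral position in the sentence that follows the hemodynamic endpoints. On its natural reading, NYHA is pooled.
- **Baseline summaries.** Protocol 14.4.1 summarizes baseline clinical variables, the categorical ones as frequencies and percentages. The SAP 7.5 list is open ("Information to be summarized includes, but is not limited to") but does not name NYHA.
- **Missing data.** SAP 7.4 leaves a subject with missing data out of the analysis affected and reports how many were included. Under Protocol 10.3.8.3 and Table 6, an explanted subject exits the study.

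**The concern.** The study exists to see whether the change of stent material harms safety or performance (Protocol 5.2), and NYHA class is one of the two parts of the performance objective. A class distribution at follow-up depends heavily on the classes in which subjects entered, and the eligibility criteria set no NYHA limit. Without pairing, the report cannot count the subjects who got worse or failed to improve after surgery, who are the ones a safety reader would want to see.

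The denominator adds to this. Subjects who died or lost the valve have no later NYHA class and drop out. If they were doing worse than the rest, the remaining percentages look better than the experience of the implanted cohort.

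**Working it through.** **The plan's own figure.** None is given for NYHA. The only computed sample size is 89, for the primary endpoint. It reproduces: with an exact one-sided 95% lower limit at 97%, the width is 0.0497 at n = 89 and 0.0501 at n = 88. No sample size rests on the secondary endpoints, so nothing here changes it.

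**What the percentages determine.** Let B_k and F_k be the cumulative percentages in class k or better at baseline and at follow-up for the same subjects, with B_0 = F_0 = 0. Over all pairings consistent with the two distributions:

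- minimum improved = max(0, max over k of F_k − B_k); maximum improved = 100 − max over k of (B_k − F_(k−1))
- minimum worsened = max(0, max over k of B_k − F_k); maximum worsened = 100 − max over k of (F_k − B_(k−1))

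The documents give no NYHA distribution, so these are assumed. Follow-up is 60/30/8/2% in classes I to IV, so F = 60, 90, 98, 100.

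| Assumed baseline I/II/III/IV | B_k | Improved | Worsened |
|---|---|---|---|
| 10/30/50/10% | 10, 40, 90, 100 | 50–90% | 0–20% |
| 60/30/8/2% | 60, 90, 98, 100 | 0–40% | 0–40% |
| 80/15/4/1% | 80, 95, 99, 100 | 0–20% | 20–40% |

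First row worked through:

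- F_k − B_k = 50, 50, 8, 0, so at least 50% improved.
- B_k − F_(k−1) = 10, −20, 0, 2, so at most 100 − 10 = 90% improved.
- B_k − F_k is never positive, so the minimum worsened is 0%.
- F_k − B_(k−1) = 60, 80, 58, 10, so at most 100 − 80 = 20% worsened.

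Two results follow. Follow-up percentages alone do not fix the direction of change: the first and third rows share them and point opposite ways. Adding the baseline percentages identifies the row, but within a row the share who worsened is still known only to within 20 percentage points (first and third rows) or 40 (second). Only pairing gives the count.

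**Denominator.** As an illustration, take the minimum of 100 implanted and the 10% first-year attrition allowed in Protocol 14.2.2, leaving 90 with data. If 54 of them are in class I, the planned table shows 54/90 = 60%; of those implanted it is 54/100 = 54%. The other 10 may have died, been explanted or simply missed the visit, and the planned NYHA table does not say which.

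**Precision of the added table.** With 89 paired subjects (assumed), exact two-sided 95% intervals for the proportion improved would be about 39–60% for 44/89, 59–79% for 62/89 and 82–95% for 80/89. That is adequate for description overall, and less so within each position.

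**The case against.** The strongest reply is that the analysis matches the endpoint and the objective. The endpoint is class at follow-up, and the aim is descriptive: "The secondary objective of the study is to characterize the clinical performance of Mosaic and Hancock II valves containing PEEK stent material at 1 year". No NYHA hypothesis is set, so no test is invalid and no estimator contradicts its definition. This stands. The gap is one of pre-specified reporting.

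A reader might go further and infer that the endpoint cannot show improvement or worsening at all. The documents do not support that. Percentages at years 1, 2 and 3 can show group drift between visits. Protocol 14.4.1, the open list in SAP 7.5 and the frequency-table sentence in SAP 7.6.2.3 all leave room for a baseline NYHA table, which would reveal the net shift. What remains missing is the individual transitions.

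Nor does the plan merge classes I and II or label any class a success; it reports each class separately. The subject's own baseline is also not the only conceivable reference, since the Protocol uses historical data for other endpoints.

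It is also fair to say that change from before surgery mainly reflects replacement of a diseased valve, so a shift table cannot separate PEEK from the previous stent material. That stands and limits what the fix can claim. Finally, the number included in each analysis will be reported, and valve-related deaths and explants are counted in the primary endpoint. This softens the denominator point, but the NYHA percentages themselves still do not account for those subjects.

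**Conclusion.** The point holds as a modest but real gap in a descriptive secondary endpoint. Both documents collect baseline NYHA class and then specify an analysis that does not use it for within-subject change, names no NYHA reference value, and covers only subjects with data. Under the assumed distributions, even baseline and follow-up tables side by side leave the proportion worsened uncertain by 20 to 40 percentage points; the real range depends on distributions that the documents do not give. The reading that by-position results exclude NYHA rests on sentence order in SAP 7.6.2.3. The primary endpoint and the sample size are unaffected. Closing the gap would improve the description of functional outcome. It would not show whether PEEK itself changed that outcome, which would need a named historical NYHA comparator.

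**What to change.** In SAP 7.6.2.3 and Protocol 14.3.1.1, keep the per-visit percentages and add text such as:

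> NYHA class at 1, 2 and 3 years will be cross-tabulated against baseline class, overall and by aortic and mitral position. The number and percentage of subjects improved by at least 1 class, unchanged, and worsened by at least 1 class will be reported. Death before the visit, explant before the visit, and missing will be shown as separate categories. The denominator is the implanted population. Change from baseline mainly reflects valve replacement and does not by itself attribute an effect to PEEK.

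The cost is one additional table from data already collected, with no new visits, tests, hypotheses or subjects. The drawback is small cells by position, which is acceptable in a descriptive display. If the sponsor wants NYHA to inform the comparison with the previous stent material, a historical NYHA source would have to be named as well; the shift table does not replace it.

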**Table 1. Mosaic models, available sizes and diameters**

Model	(1) Valve Size (Stent OD  ) ( $\pm 0.5$ mm)	(2) Orifice Diameter (Stent ID) ( $\pm 0.5$ mm)	(3) Suture Ring Diameter ( $\pm 1$ mm)	(4) Valve Height ( $\pm 0.5$ mm)	(5) Aortic and Ventricular Protrusion ( $\pm 0.5$ mm)
Aortic Valve (305)	19	17.5	25	13.5	11.0
	21	18.5	27	15.0	12.0
	23	20.5	30	16.0	13.5
	25	22.5	33	17.5	15.0
	27	24.0	36	18.5	15.5
	29	26.0	39	20.0	16.0
Aortic Ultra (305)	19	17.5	24	13.5	11.0
	21	18.5	26	15.0	12.0
	23	20.5	28	16.0	13.5
	25	22.5	30	17.5	15.0
	27	24.0	32	18.5	15.5
	29	26.0	34	20.0	16.0
Mitral Valve (310)	25	22.5	33	18.0	13.5
	27	24.0	35	19.0	14.0
	29	26.0	38	20.5	15.5
	31	28.0	41	22.0	17.0
	33	30.0	43	23.0	17.5

Stent OD: equivalent to annulus diameter.

Disposable Cinch® Advanced Implant System (Cinch II for aortic valves and Cinch for mitral valves) holders are sutured to both aortic and mitral valves. These holders incorporate a ratchet mechanism, which, after screwing the valve holder onto the handle, is actuated by further handle rotation. This then causes the stent posts to be drawn inward, easing valve implantation. In the case of the mitral valve, the suture attaching the valve holder also prevents looping of the surgeon's sutures during implantation.

[figure not shown]
The disposable holders are designed to fit the reusable Valve Handles (Model 7639). Each valve handle is also used with the Mosaic valve obturators (Model 7310) for measuring the mitral annulus. Proper valve size selection is an important part of heart valve replacement. The size of the Mosaic to be implanted is determined by the surgeon with the aid of Mosaic Cinch aortic sizers (Model 7308C), Mosaic Ultra aortic sizer (Model 7308U) for the aortic valve or Obturators (Model 7310) for the mitral valve.

Mosaic Obturator Models 7310 (mitral) are manufactured using transparent polysulfone. These obturators are intended to aid the surgeon in selecting the optimum size for Mosaic mitral valve and are intended for use only with this valve. The Medtronic Valve Handle Model 7639 is composed of surgical stainless steel and can be screwed on the obturator for sizing or the Cinch holder for valve cinching/ratcheting for implantation. A thinned section of the handle allows for repeated bending to facilitate implantation of the valve. The handle is offered in two lengths (234 mm and 368 mm).

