#### **10.3.8.1. Index Procedure**

The Index Procedure is defined as the procedure where the Mosaic or Hancock II valves with PEEK material is implanted or attempted in the study subject.

The following implant data will be collected and recorded for the implant procedure.

- Procedure details including condition of explanted valve and any additional procedures or interventions (as applicable)

- Serial number, valve size and disposition of implanted valve or opened valve packages
- Documentation of device failure or malfunction (as applicable)
- Peri-operative Transesophageal Echocardiography (TEE)
- Adverse events/device deficiency

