#### **14.3.1. Secondary Endpoints**

The clinical performance endpoints are:

- NYHA Functional Classification (at 1 year and annually thereafter through 3 years)
- Clinically acceptable hemodynamic performance as measured by the following hemodynamic measurements obtained from echocardiography at discharge or  $\leq 30$  days (whichever comes first), 1 year and annually thereafter through 3 years):
  - effective orifice area (EOA)
  - effective orifice area index (EOAI)
  - peak pressure gradient
  - mean pressure gradient
  - performance index
  - cardiac output
  - cardiac index
  - valve regurgitation

No specific hypotheses have been set for the analysis of hemodynamic performance of Mosaic and Hancock II valves containing PEEK stent material at 1 year post-implant. No sample size determination is based on these secondary endpoints.

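### Haemodynamic endpoints are summarised by valve position but not by labelled valve size, so for EOA, EOAI and gradients a difference from historical data cannot be separated from a difference in size mix

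*SAP*

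**What the plan says.** SAP 7.6.2.3 gives the summary rule for the echocardiographic endpoints: "Hemodynamic Performance endpoints will be summarized as with continuous data. These data will be summarized by aortic and mitral position". Position is the only stratum named. SAP 7.2 adds that continuous variables are reported with mean, SD, median, interquartile range, minimum and maximum.

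The comparison itself is in Protocol 14.3.1.1: "Hemodynamic performance will be qualitatively compared with historical clinical performance data for Mosaic and Hancock II valves from literature". The same sentence adds current treatment guidelines as a second benchmark for clinically acceptable performance. The SAP does not repeat or develop this comparison.

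The comparison is descriptive. SAP 7.6.2.1 says "No specific hypotheses have been set for the analysis of hemodynamic performance of Mosaic and Hancock II valves containing PEEK stent material", and Protocol 14.3.1 says "No sample size determination is based on these secondary endpoints".

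The data for a by-size summary will exist. Protocol 10.3.8.1 lists among the implant data "Serial number, valve size and disposition of implanted valve or opened valve packages". Protocol Table 1 ("Mosaic models, available sizes and diameters") and Table 2 give the orifice diameter for every labelled size.

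**The concern.** The study has no concurrent control. Apart from the guideline benchmark, the comparison with historical Mosaic and Hancock II data is the only planned route from the echo measurements to a statement about the new stent material. EOA, EOAI and gradients can be expected to depend on the size of the implanted orifice. If each position is summarised over all its sizes, the summary reflects whichever sizes happened to be implanted, and the historical series carries its own size mix.

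Nothing in the design fixes the mix. Protocol section 7 limits implants per site and in total, but sets no quota by size, model or position. The two models also differ in range: Mosaic aortic valves start at size 19, Hancock II aortic valves at 21.

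The error can go either way. More small valves than in the historical series would make PEEK look worse, and more large valves could hide a real deterioration.

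**Working it through.** **1. The plan's own figure.** The documents calculate no size or precision for haemodynamics. The only calculated size is 89 subjects at 1 year for the primary endpoint (SAP section 6). It reproduces: with an event-free proportion of 97%, the exact one-sided 95% lower limit lies 4.97 percentage points below at n = 89 and 5.01 at n = 88. It is used here only to count subjects per cell.

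**2. Orifice area by labelled size.** Inputs are the orifice diameters d in Protocol Tables 1 and 2. They are the same for both models where sizes overlap, and the same for Ultra and standard aortic valves. Area = (π/4) × d².

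| Position | Labelled sizes | d (mm) | Area (cm²) |
|---|---|---|---|
| Aortic | 19, 21, 23, 25, 27, 29 | 17.5, 18.5, 20.5, 22.5, 24.0, 26.0 | 2.41, 2.69, 3.30, 3.98, 4.52, 5.31 |
| Mitral | 25, 27, 29, 31, 33 | 22.5, 24.0, 26.0, 28.0, 30.0 | 3.98, 4.52, 5.31, 6.16, 7.07 |

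Largest to smallest: aortic (26.0/17.5)² = 2.21; mitral (30.0/22.5)² = 1.78. One labelled size changes area by 12% to 23% (aortic) or 14% to 17% (mitral).

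**3. Shift in a pooled mean from size mix alone.** The documents give neither this study's expected mix nor the historical one, so the mixes below are assumptions (per cent of implants, smallest to largest size). Pooled mean area = Σ w × area. The gradient proxy is Σ w × 1/area², which assumes equal flow across sizes.

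| Position | Assumed mix | Mean size (mm) | Mean area (cm²) | Area vs middle mix | Gradient proxy vs middle mix |
|---|---|---|---|---|---|
| Aortic | small: 15, 30, 30, 15, 8, 2 | 22.54 | 3.222 | -8.2% | +19.6% |
| Aortic | middle: 5, 20, 35, 25, 12, 3 | 23.56 | 3.509 | reference | reference |
| Aortic | large: 2, 8, 15, 30, 30, 15 | 25.46 | 4.105 | +17.0% | -26.2% |
| Mitral | small: 30, 35, 20, 10, 5 | 27.50 | 4.807 | -6.8% | +14.5% |
| Mitral | middle: 15, 30, 30, 17, 8 | 28.46 | 5.159 | reference | reference |
| Mitral | large: 5, 10, 20, 35, 30 | 30.50 | 5.989 | +16.1% | -25.7% |

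Labelled sizes are 2 mm apart. The small and large mixes therefore differ from the middle one by about half a size to about one size on average. The stent has no effect in any row.

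**4. Subjects per cell if size is used.** There are 6 aortic + 5 mitral = 11 position-by-size cells: 89/11 = 8.1 and 110/11 = 10.0 if spread evenly. Splitting by model gives 21 cells (Mosaic 6 + 5, Hancock II 5 + 5): 89/21 = 4.2 and 110/21 = 5.2.

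**The case against.** The best defence is that this is a qualitative, secondary description with no hypothesis, so no decision rule or error rate is affected. The protocol does not say that pooled means are the quantity compared, and it does not exclude a comparison by size. Protocol sections 14 and 14.1 allow further exploratory analyses. Protocol 5.2 gives a reason for combining valves: the stents are identical in configuration and material, and bench tests support PEEK and AHP equivalence at every position and size.

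Part of this stands. The pooling is by omission rather than by an explicit rule, and the consequence is for interpretation only. The rest does not answer the point. An allowance for exploratory work does not pre-specify the table. Bench equivalence of the two materials does not make valves of different sizes haemodynamically alike, or make two cohorts' size mixes equal.

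Three stronger readings are tempting and should not be drawn:

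- A reader might infer that size mix distorts the comparison as much as the stent does, or that it is the main confounder. The documents give no size mix, no haemodynamic values by size and no expected stent effect, so the two cannot be ranked.
- A reader might square the area ratios and infer gradient bias of up to 2.21² = 4.9-fold (aortic) or 1.78² = 3.2-fold (mitral). Those figures compare the smallest with the largest single valve at equal flow. Two cohort averages would differ that much only if one cohort were all smallest and the other all largest.
- A reader might apply the point to all eight haemodynamic measures. Cardiac output, cardiac index and regurgitation should depend less on size, and performance index, which the documents do not define, may already be partly normalised for size.

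**Conclusion.** The point holds for EOA, EOAI and peak and mean gradient. Under the summary that the SAP specifies, a difference from historical values, or its absence, cannot be attributed to PEEK rather than to size mix. The plausible scale is a shift in pooled mean orifice area of about -8% to +17% (aortic) or -7% to +16% (mitral), and in the gradient proxy of about +20% to -26% or +15% to -26%.

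These figures rest on assumed mixes, on geometric orifice area standing in for EOA, and on equal flow for the gradient proxy. They show that the problem is not negligible; they do not estimate its size in this study. The 2.2-fold and 1.8-fold area ratios come directly from the protocol's tables, but they describe extremes between single valves.

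The change should be made because the historical comparison is weak without it. It does not touch the primary endpoint, the sample size or any error rate.

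**What to change.** - **SAP 7.6.2.3:** add a descriptive table of EOA, EOAI, peak gradient and mean gradient by labelled valve size within position at each visit, with n in every cell. Split further by model only where counts allow.
- **Protocol 14.3.1.1:** state that the historical comparison is made size by size. Where cells are small and the literature reports size-specific means h_s, standardise them to this study's mix, Σ (n_s/N) × h_s, and compare that value with the study's pooled mean. Where the literature has no size-specific means, say so and show this study's size distribution beside the comparison.

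No new data are needed, because size is recorded at implant and the core lab supplies the echo values. The costs are one further table per visit, the extraction of size-specific historical values, and an amendment to the protocol text. The main downside is small cells: about 8 to 10 subjects each if evenly spread, fewer at the extreme sizes and after missed echoes, and only about 4 to 5 with a full split by model. The table should be labelled descriptive, with no tests between sizes.
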